##### **Caregiver**

- Recognized/intends to be recognized as proxy for patient's MyGeisinger Account (cases only)
- English-speaking

##### **Providers:**

- Any health care provider within Medical Oncology or Radiation Oncology at GMC, where FCA is standard of care, who has a patient enrolled.

#### **4.2.3 Exclusion Criteria**

##### **Patients**

- Patients who are not diagnosed with lung cancer.
- Patients who are diagnosed with lung cancer and are on active Oncology Care exceeding 3 weeks ( $> 27$  days).

##### **Providers:**

- Any healthcare provider not within the Medical Oncology or Radiation Oncology departments.
- Any healthcare provider within Medical Oncology or Radiation Oncology who does not have a patient enrolled (Case Dyad).

### **4.3 Recruitment**

#### *Cases (GMC):*

Eligible patients will be identified through a database that runs an algorithm designed to consume aggregate electronic health record data to find potential participants that meet inclusion (and do not meet exclusion) criteria at the treatment site. A weekly occurrence of the eligibility list will occur however, depending on the rate of recruitment the study team will determine whether this needs to occur more frequently

The research assistants will verbally review the list of potential participants with clinical staff to validate that patients on the list meet inclusion criteria and can be approached for recruitment. The research assistant will be available to speak with patients before or after their scheduled medical appointments.

For the purpose of study awareness, informational flyers will also be available to patients in the exam rooms, waiting rooms, and Oncology Care's MDC. (**Attachment W: Recruitment Flyer - Cases**).

MDC lung cancer clinic is held weekly as a multidisciplinary treatment with a goal of prospective treatment planning to increase alignment with nationally recognized guidelines for cancer care. Patients and their families meet with the MDC team to review their diagnosis and determine the appropriate treatment plan. MDC team members include surgical, medical and radiation oncology, pathology, radiology, dieticians, case management, oncology nursing (including nurse navigators) and pharmacy.

*Controls (GCMC and GWV):*

For every Case patient enrolled at GMC, a data analyst will run the algorithm to consume aggregate electronic health record data to find and create a database of potential participants that meet inclusion (and do not meet exclusion) criteria at control sites. A weekly occurrence of the eligibility list will occur however, depending on the rate of recruitment the study team will determine whether this needs to occur more frequently. Study team members will apply a 1:1 case-matched control strategy to identify potential control patients that match case patients in terms of sex, age category, lung cancer histology, and lung cancer clinical and/or pathological staging information. This will be done after the Case patient-participant has a Case caregiver-participant consented to ensure that Case Dyads are enrolled and available for matching. If a Case patient-participant has enrolled but the Case caregiver-participant fails to enroll, the Case patient-participant will still be eligible for the study however the study team will recruit a replacement Case Dyad with the goal of enrolling 25 Case Dyads. Case patient-participants without caregiver-participants will be removed from analyses. Similarly, if a Control patient-participant consents but a Control caregiver-participant fails to enroll, the study team will identify a replacement Control Dyad with the goal of enrolling 25 Control Dyads. Research assistants will use the database to run weekly reports to identify potential control patients at GCMC or GWV to approach for recruitment. The research assistants will verbally review the list of potential participants as well as the weekly MDC list at GCMC and GWV with clinical staff to validate that patients on the list meeting inclusion criteria and can be approached for recruitment. The research assistant will be available to speak with patients before or after their scheduled medical appointments.

For the purpose of study awareness, informational flyers will also be available to patients in the exam rooms, waiting rooms, and through Oncology Care's MDC (**Attachment X: Recruitment Flyer - Controls**).

Demographic information will be collected on all eligible participants who are asked to participate. This information will be collected as part of the Pre-Treatment Survey for Case

Dyads and Post-Treatment Survey for Control Dyads. Patients and caregivers that are approached, but decline participation will be asked to complete an anonymous brief demographic survey (**Attachment Z: Non-Participant Survey**).

Providers (GMC only):

Providers will be invited to take part in the study by receiving an invitation e-mail (**Attachment AA: Provider Interview Email Invitation**) from the study team. We will use an opt-out approach when inviting providers to participate. Providers who are not interested in participating are asked to respond to the e-mail invitation within 14 days of receipt. Those who do not respond within the 14-day window will be scheduled for an interview.

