***Observe quality and performance indicators among usual oncology care in similar patient-caregiver population to compare with cases.*** From non-treatment sites, identify, recruit, consent, and enroll persons with lung cancer (newly diagnosed or recent recurrence of disease) and their caregivers into the evaluation study. Recruitment will continue until 25 patients and 25 caregivers are enrolled (Control Dyads). Electronic health records for patients (appointment, clinical, and patient-reported data such as the M.D. Anderson Symptom Inventory that is standard of care) and study questionnaires will be used to evaluate quality and performance indicators however, questionnaires will be fielded at the post-period only. Non-treatment sites will not provide FCA as standard of care and function as control sites. These sites will include Geisinger Wyoming Valley in Wilkes-Barre, PA (“GWV”), and Geisinger Community Medical Center in Scranton, PA (“GCMC”). A case-matched controlled design will be used to evaluate differences in quality and performance indicators between groups at the post-period only.

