#### **4.2.1 Approximate Number of Subjects**

Approximately 135 Geisinger subjects (65 patients and 50 caregivers) will participate in the study. Patients are able to participate independent of having a caregiver; therefore the number of Geisinger patients enrolled is reflective of this possibility. Our goal is to include 100 participants in our analysis (50 patients and 50 caregivers) organized as 25 Cases Dyads and 25 Control Dyads. We will enroll 20 Geisinger providers in the treatment site who will participate in this study. If a caregiver receives care at Geisinger, his/her patient-related records are not of interest to or related to this study.

Background Logic Regarding Sample Size: The number of eligible lung cancer patients was estimated from a twelve-month report (May 2016-April 2017) ("Estimate Time Period") from each respective hospital which informed the Exploratory Evaluation Study design. Patients were included if, during the Estimate Time Period, they had an active lung cancer diagnosis on the EHR problem list and had an encounter at one of the following oncology departments (Hematology Oncology Danville, Radiation Oncology Danville, Hematology Oncology GWV, Radiation Oncology GWV) ("Inclusion Criteria"). There were 153 eligible patients from GMC ("GMC Lung Cancer Patients"), 137 eligible patients from GWV ("GWV Lung Cancer Patients"), and 21 eligible patients from GCMC ("GCMC Lung Cancer Patients") for potential inclusion in the Exploratory Evaluation Study and Phase III FCA expansion rollout. Given that the Exploratory Evaluation Study period is 6 months, the estimated count of eligible patients is reduced by 50% to 77 Case patients at GMC, 69 Control patients at GWV and 11 Control patients at GCMC.

Based upon Phase II enrollment at GMC, it is anticipated that 37% of eligible GMC Lung Cancer Patients (i.e., 28) will consent to participate in the evaluation and enroll as a Dyad. Based on Phase II enrollment at GMC, 100% of these patients will identify a caregiver who consents to

*Version 1.10 – 5.24.2018*

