participate as part of a dyad. Based on Phase II observations, 90% of these Dyads (i.e., 25) will complete an intensive 8-week treatment cycle. Recognizing variability in the incidence of disease, we chose the more conservative sample size of 25 patients enrolling in the study as part of a dyad for each arm thus resulting in 25 Case Dyads and 25 Control Dyads or 100 patient-caregiver participants. Based on Phase II observations, 90% are estimated to complete the 8-week treatment cycle and study.

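### Section 4.2.1 makes no allowance for the four-factor 1:1 matching in 4.3; if a match means the same category on all four factors, about 16–19 of 25 Cases would be matched, and no rule covers the rest

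*Combined protocol and SAP*

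**What the plan says.** Section 4.3 (Recruitment, Controls) has the team "apply a 1:1 case-matched control strategy to identify potential control patients that match case patients in terms of sex, age category, lung cancer histology", and also on clinical and/or pathological stage. The search for a Control starts once the Case patient's caregiver has consented. The section sets a goal of 25 Control Dyads, and Specific Aim 3 says "Recruitment will continue until 25 patients and 25 caregivers are enrolled (Control Dyads".

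Section 4.2.1 halves twelve-month counts ("Given that the Exploratory Evaluation Study period is 6 months") to "77 Case patients at GMC, 69 Control patients at GWV and 11 Control patients at GCMC". It then takes the Case arm through consent ("37% of eligible GMC Lung Cancer Patients (i.e., 28) will consent to participate"), caregiver participation ("100% of these patients will identify a caregiver who consents to") and completion ("90% of these Dyads (i.e., 25) will complete an intensive 8-week treatment cycle"). Both arms are set at 25 dyads. There is no corresponding chain for Controls, matched or unmatched.

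Section 4.3 gives no age bands, histology groups or stage groups. It gives no tolerance, no priority among the factors and no rule for a Case without a match. Its only replacement rule for Controls covers a caregiver who does not enroll. Section 4.8.1 compares Cases with Controls by chi-square, t or non-parametric tests, with no covariates and no use of the pairs.

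**The concern.** The pool looks adequate if all that is needed is 25 consenting Controls. Matching asks for more: the consenting Controls must fall in the same sex, age, histology and stage cells as 25 particular Cases. A margin of about five people (30 against 25) is thin once it is spread over at least 16 cells.

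The stake is the primary comparison. Allocation is by clinic, Controls have no baseline survey, and no adjustment is planned, so matching is the main protection against case-mix differences between sites. If it falls short with no rule in place, either recruitment stops early or someone decides, knowing the Case, which factor to ignore. The delivered comparison could then not be reconstructed from the protocol.

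**Working it through.** **1. Reproduce the plan's figures (4.2.1).** 153/2 = 76.5, 137/2 = 68.5 and 21/2 = 10.5, which round to 77, 69 and 11. Then 0.37 × 77 = 28.5 (stated 28) and 0.90 × 28 = 25.2 (stated 25). The Case chain reproduces.

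**2. Controls without matching.** The pool is 69 + 11 = 80. Applying 37% to Controls is an assumption; the protocol gives that rate for the treatment site only. Expected consenters: 80 × 0.37 = 29.6. For Binomial(80, 0.37), P(at least 25) = 0.88. If 90% completion is also required, the rate is 0.37 × 0.90 = 0.333, the expected number is 26.6 and P(at least 25) = 0.69.

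**3. Controls with same-category matching.** Assumptions: two levels per factor, so 2 × 2 × 2 × 2 = 16 cells; the same case mix at all sites; timing ignored. Draw 25 Cases over the cells, draw Binomial(80, 0.37) consenting Controls over the same cells, and count

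pairs = sum over cells of min(Cases in cell, Controls in cell).

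With equal cells there are on average 25/16 = 1.6 Cases and 29.6/16 = 1.85 Controls per cell. The chance that a given cell has no consenting Control is (1 − 0.37/16)^80 ≈ 0.15. Simulation (40,000 runs) gives:

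| Split on each factor | Mean pairs of 25, pool 80 | Chance all 25 matched | Mean pairs, pool 93 |
|---|---|---|---|
| 50/50 | 16.1 | below 0.1% | 17.5 |
| 60/40 | 16.3 | below 0.1% | 17.8 |
| 70/30 | 17.2 | below 0.1% | 18.6 |
| 80/20 | 18.7 | about 0.2% | 20.0 |
| 90/10 | 20.9 | about 3% | 21.8 |

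The last column uses the seven-month recruitment period in 4.4.2: 80 × 7/6 ≈ 93. With that pool the chance of matching all 25 reaches about 6% at 90/10 splits. Requiring 90% completion with the pool of 80 lowers the mean to about 15–18 for splits up to 80/20.

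**4. Sensitivity to Control consent (pool 80, 16 cells).** At 50% consent, 18.9–19.9 pairs for splits up to 70/30. At 60%, about 20.5–23 across all the splits. At 75%, 22.3–22.5 for splits up to 70/30. If all 80 consented, about 24 pairs, with a 30–43% chance of matching all 25.

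**5. Sensitivity to the number of cells (37% consent, pool 80).** Eight equal cells give about 19 pairs. One scheme with 32 cells gives about 14–15, and 72 cells about 7–10. These level counts are illustrations; the protocol states none.

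**The case against.** The strongest objection is that the protocol never calls the match exact. It names factors and leaves closeness open, so a coarse or partial match could reach 25. That stands. A reader might infer from the calculation that 25 matched Control Dyads cannot be obtained, but the documents do not support that. What they support is that same-category matching would very probably fall short, and that no looser rule is written down.

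Second, 37% comes from earlier enrollment at the treatment site. Controls have a lighter task: one survey, with no portal account, proxy access or application use required. Their consent may be higher. That also stands, and it is why a range is shown. A better rate shrinks the gap without closing it: even with every Control consenting, the chance of a full set of 25 stays under one half.

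Third, a reader might want a lower yield because Controls are sought only after the Case Dyad consents. The direction is right. Its size depends on how long a Control stays approachable, and since patients merely scheduled to start treatment also qualify, the documents do not fix that window. No timing figure is relied on here.

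Fourth, the planned tests do not use pairs, so an unmatched Case loses no data; all tests are labelled descriptive, and section 4.1 already concedes that patient factors may explain any association. This limits the harm to comparability. It does not supply the missing rule.

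One consideration runs the other way. The 80 are patients with an active problem-list diagnosis and an oncology encounter, not patients about to start or within 27 days of starting treatment, so the usable pool may be smaller.

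**Conclusion.** The concern holds in conditional form. If a match means the same category on all four factors, with two levels each, equal case mix across sites and 37% Control consent, the protocol's pool gives about 30 Controls and about 16–19 matches for 25 Cases, rising to about 21 at very uneven splits. At 60% consent it gives about 20.5–23. Matching all 25 at 37% is very unlikely: mostly below 0.3%, and about 3% at 90/10 splits. Twenty-five Controls without matching are within reach (P about 0.88). The expected outcome is therefore a shortfall of matched dyads, or a match relaxed without a rule, followed by an unadjusted primary comparison. The stated feasibility arithmetic contains no error; the matching step is simply left out of it.

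This uses the target of 25 in 3.3, 4.2.1 and 4.3. Section 4.8.2 gives 50 Control Dyads, which exceeds the 29.6 expected even without matching and needs reconciling separately.

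**What to change.** - **4.3:** define coarse categories for age, histology and stage; fix the order in which factors are relaxed when no full match is available; and set a rule or date after which an unmatched slot opens to any eligible Control.
- **4.8.1:** adjust the primary Case-versus-Control comparison for sex, age, histology and stage, and report the numbers of full, partial and unmatched pairs. Histology and stage are needed for matching but are not named in the 4.8.1 data list, so add them.
- **4.2.1:** state the expected matched yield over a range of Control consent rates, since none is given.

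Individual matching can stay. Frequency matching on coarse strata is an alternative with its own trade-offs and is not required.

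The cost is protocol wording, a looser match for some Cases and a few degrees of freedom. With 50 dyads and one term per factor, residual degrees of freedom fall from 50 − 2 = 48 to 50 − 6 = 44.

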***Observe FCA in clinical oncology practice to evaluate quality and performance indicators.***

Integrate exposure to FCA as standard of care in a conveniently selected clinic for persons with lung cancer and their caregivers. Clinicians in this clinic have contributed to the development and testing of FCA as standard of care at Geisinger Medical Center in Danville, PA (“GMC”). This clinic will serve as the treatment site. Electronic health records and FCA dashboard analytics will be used to evaluate clinician use of the tool. Clinicians at the treatment site will provide interview data describing their experience related to quality, FCA adoption and implementation into workflow integration at the post-period;

### 3.2 Specific Aim 2

***Observe FCA use among patients and caregivers to evaluate quality and performance indicators associated with oncology care.*** From the treatment site, identify, recruit, consent and enroll persons with lung cancer (newly diagnosed or recent recurrence of disease) and their caregivers. Recruitment will continue until 25 patients and 25 caregivers (Case Dyads) are enrolled. Electronic health records for patients (appointment, clinical, and patient-reported data such as the M.D. Anderson Symptom Inventory that is standard of care) and study questionnaires will be used to evaluate quality and performance indicators. Questionnaires will be fielded with Case Dyads, as hereinafter defined, at baseline and after 8 weeks of exposure to FCA. Pre-post changes will be evaluated among cases.

### 3.3 Specific Aim 3

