#### **4.2.2 Inclusion Criteria**

##### **Patients**

- Patients who are 18 years of age or older and diagnosed with lung cancer who 1) are scheduled to start Oncology Care (chemo and/or radiation-therapies) OR 2) on active Oncology Care and recently started within 3 weeks ( $\leq 27$  days)
- Receive care at GMC, GWV, or GCMC
- English-speaking
- Established/intends to establish a MyGeisinger Account (cases only)

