#### **I. Patient:**

- Study ID
- Patient Survey Responses
- Date of birth
- Date of death (where applicable)
- Gender

- Treatment Location (GMC, GWV, GCMC)
- Problem list diagnoses
- Outpatient Encounters
  - Date
  - Flag for interpreter used
    - # distinct specialties seen
  - Visit type
  - Provider ID
  - Provider type
  - Clinic/department/location/specialty
  - Diagnosis codes associated with visit (flag primary)
  - Disposition (completed/no-show/cancel)
- Inpatient Encounters
  - Admission date
  - Diagnosis codes associated with discharge (flag primary)
  - Location (e.g. ICU)
  - Discharge date
- ED encounter data
  - Date
  - Diagnoses associated with visit (flag primary)
  - Flag if resulted in an admission
  - MD Anderson Symptom Inventory
- FCA (Harmonized Care) Usage
  - Dates of log-on
  - All features accessed in the application including dates accessed and number of views
  - Interest and Information
    - Number of topics added
    - Number of events added
    - Number of photos added
  - Appointments
    - Number of calendars added
    - Number of appointments added
  - Care Partners
    - Number of care partners added
  - Medication Management
    - Number of medications scheduled
    - Number of questions added
  - Notes
    - Number of private notes
    - Number of shared notes
  - Profile

- Number of profile pictures added

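### Treatment modality and new-versus-recurrent disease are neither matched on nor used in the Case–Control analysis, so a site difference in either would enter the primary contrast uncorrected

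*Combined protocol and SAP*

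**What the plan says.** **Who may enter.** Section 4.2.2 admits patients who "are scheduled to start Oncology Care (chemo and/or radiation-therapies"), and also those "on active Oncology Care and recently started within 3 weeks". Chemotherapy alone, radiation alone and both together are all eligible. Aim 2 (section 3.2) is to "enroll persons with lung cancer (newly diagnosed or recent recurrence of disease) and their caregivers" at the treatment site. Aim 3 (section 3.3) uses the same description for the control sites: "enroll persons with lung cancer (newly diagnosed or recent recurrence of disease) and their caregivers into the evaluation study".

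**How Controls are chosen.** Section 4.3 applies 1:1 matching to find Controls who "match case patients in terms of sex, age category, lung cancer histology, and lung cancer clinical and/or pathological staging information". Section 4.5 adds an attempt, where possible, to pair remote caregivers with remote caregivers. No other matching factor is named.

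**How the arms are formed and measured.** All Cases come from GMC and all Controls from GWV or GCMC (section 4.2), without randomisation (section 4.1). Controls are surveyed after the period only (section 3.3). Section 4.1 defends this by expecting the groups not to differ at baseline.

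**What is collected.** The patient list in section 4.8.1 has no field for treatment modality or for new versus recurrent disease. The nearest items are encounter-level visit type and "Clinic/department/location/specialty" for modality, and "Problem list diagnoses" with visit diagnosis codes for recurrence. The Data Sources text also names Aria, the radiation oncology system.

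**How the arms are compared.** For Case against Control, section 4.8.1 names chi-square tests, t-tests and non-parametric univariate tests. The optional sensitivity strata are level of FCA use and opportunity time for exposure. ANCOVA is mentioned only for the pre-post change within Cases.

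**The concern.** The primary question (section 4.6) covers coordination of care, satisfaction, quality of life, caregiver burden, symptoms and scheduled versus missed appointments. Modality plausibly bears on all of these, because it affects how many departments and visits have to be coordinated and what symptoms the patient has. The Quality of Care part of section 2 itself presents combined-modality therapy as a setting where better coordination may help.

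A Case on combined therapy can be paired with a Control of the same sex, age category, histology and stage who receives one modality. A newly diagnosed Case can be paired with a Control in recurrence. If the treatment mix at GMC differs from that at GWV and GCMC, part of the Case–Control difference would reflect that mix and be read as an effect of FCA exposure.

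One listed measure is also tied to modality for its availability. Section 4.8.1 describes the MD Anderson Symptom Inventory as routine during active chemotherapy, so radiation-only patients may lack it and the arms could contribute different subsets.

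**Working it through.** **1. The plan's own numbers.** The documents give no power calculation (section 4.8.2), so the only figures to reproduce are the feasibility counts in section 4.2.1.
- Eligible at GMC: 153 × 0.5 = 76.5, stated as 77.
- Consenting: 77 × 0.37 = 28.5, stated as 28 (unrounded, 76.5 × 0.37 = 28.3).
- Completing: 28 × 0.90 = 25.2, stated as 25.

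These reproduce. Section 4.8.2 instead states 50 dyads per arm. That conflict needs reconciling separately; both sizes are shown below.

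**2. Is there any step that would correct an imbalance?**
- Randomisation: none (4.1).
- Matching: four patient factors, neither of these two (4.3).
- Baseline survey in Controls: none (3.3).
- Covariates or strata in the Case–Control comparison: none for these factors (4.8.1).

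Histology and stage probably reduce a modality difference, but nothing in the plan ties either to a single modality, and recurrence is not a matching factor.

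**3. Illustrative size.** The documents give no modality shares and no modality effects, so both inputs are assumptions.

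Bias = (difference in modality share between arms) × (modality effect in SD units).

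| Imbalance | Effect 0.3 SD | Effect 0.5 SD | Effect 0.8 SD |
|---|---|---|---|
| 20 points | 0.06 | 0.10 | 0.16 |
| 30 points | 0.09 | 0.15 | 0.24 |
| 40 points | 0.12 | 0.20 | 0.32 |

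**4. Against the precision of the comparison.** SE of a difference in two means = √(2/n) SD.
- 25 per arm: SE = √(2/25) = 0.283; 95% half-width = 1.96 × 0.283 = 0.55 SD. The bias is 0.06/0.554 = 11% to 0.32/0.554 = 58% of the half-width. With no FCA effect, a nominal two-sided 5% test would reject 5.5% to 20.5% of the time.
- 50 per arm: SE = 0.200; half-width = 0.39 SD. The rejection rate would be 6.0% to 36.0%.

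**5. Cost of adjusting.** For one binary modality covariate with an assumed 35%/65% split between arms, the correlation with arm is 0.30. Variance inflation = 1/(1 − 0.30²) = 1.10, so the SE rises from 0.283 to 0.283 × √1.10 ≈ 0.297 SD, before any gain from explained variance.

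**The case against.** **The study is exploratory and concedes confounding.** Section 4.1 says that patient factors or quality of care at the clinics may explain what is seen, and sections 4.8.1 and 4.8.2 make every test descriptive. This stands: the point is an omitted safeguard, not a concealed error. The caveat is general, however. It names neither factor and gives no way to examine them.

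**The data may already be there.** A reader might infer from the patient list that a modality imbalance could be neither seen nor corrected. The documents do not support that. Department and specialty are recorded for each encounter, section 4.2.1 shows hematology oncology and radiation oncology as separate departments at GMC and GWV, and Aria is a named source. Histology and stage are also missing from the list although they are matching factors, so absence from it does not prove unavailability. Applying section 4.2.2 already requires knowing whether and when treatment started. Section 4.8.1 promises to describe clinical information without defining it, and the survey attachments are not among the documents available. What remains is that no section plans to derive modality or to use it in the comparison, and recurrence is harder to recover from diagnosis codes.

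**Chance imbalance.** A reader might add that, even with identical practice at all sites, a gap of at least 5 of 25 arises 16% to 20% of the time at a prevalence of 0.3 to 0.5. That does not strengthen the point. The calculation treats the arms as unmatched, and chance imbalance is already inside the standard error of the univariate test. Only a systematic site difference is bias.

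**The illustrated bias is small beside the noise.** True at 25 per arm, where every value in the table lies inside the half-width. It is still a shift that more dyads would not remove.

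**Conclusion.** The point holds in a limited form. Followed as written, the plan leaves a site difference in treatment modality or disease status uncorrected in the primary contrast, and the general caveat in section 4.1 does not repair that. The documents do not show that such a difference exists, so it would be wrong to conclude that an observed Case–Control difference is treatment mix; they show only that it could be.

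The size cannot be determined from the documents. The range of 0.06 to 0.32 SD rests wholly on the assumed imbalance and effect, and it takes no credit for whatever balance the stage and histology matching brings. Adjustment would not rescue a causal reading either: every Case is at one site, so FCA and site stay inseparable whatever is done about modality.

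**What to change.** In section 4.8.1:
- Add two fields to the patient data list, taken from Epic and Aria: treatment modality at study entry (chemotherapy only, radiation only, combined) and disease status (new, recurrent).
- Tabulate both by arm.
- Add a Case–Control analysis adjusted for or stratified by them, reported beside the univariate test. Collapsing modality to combined versus single saves a degree of freedom.

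In section 4.3, preferring a same-modality Control when several candidates meet the four factors is optional and must not block enrolment. It will seldom apply: section 4.2.1 gives 69 + 11 = 80 eligible Controls, and if GMC's 37% consent rate carried over (an assumption), 80 × 0.37 ≈ 30 would consent for 25 places.

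**Cost.** A protocol amendment, two fields from systems already named as sources, and a model or stratified analysis that the plan does not now contain for this contrast. With 25 dyads per arm the adjustment uses 2 degrees of freedom (binary modality plus disease status) or 3 (three-level modality plus disease status), out of 50 − 2 = 48. The loss of precision is about that shown in step 5 of the working for one binary covariate.
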